The trial will be carried out in accordance with International Council on Harmonisation Good Clinical Practice (ICH GCP) and the following:

- United States (US) Code of Federal Regulations (CFR) applicable to clinical studies (45 CFR Part 46, 21 CFR Part 50, 21 CFR Part 56, 21 CFR Part 312, and/or 21 CFR Part 812)

National Institutes of Health (NIH)-funded investigators and clinical trial site staff who are responsible for the conduct, management, or oversight of NIH-funded clinical trials have completed Human Subjects Protection and ICH GCP Training.

The protocol, informed consent form(s), recruitment materials, and all participant materials will be submitted to the Institutional Review Board (IRB) for review and approval. Approval of both the protocol and the consent form must be obtained before any participant is enrolled. Any amendment to the protocol will require review and approval by the IRB before the changes are implemented to the study. In addition, all changes to the consent form will be IRB-approved; an IRB determination will be made regarding whether a new consent needs to be obtained from participants who provided consent, using a previously approved consent form.

PROTOCOL SUMMARY

1.1 SYNOPSIS

Title:	Feasibility of Measuring Volume of Inspiration Via Non-Invasive Motion Sensors
Study Description:	This protocol is a basic physiologic proof-of-concept study enrolling normal volunteers to determine the feasibility of measuring volume of inspiration from chest wall motion measured via non-invasive thoracic motion sensors. The motion sensors are not medical devices because they are not intended to diagnose a disease or condition or to cure, mitigate, treat or prevent disease. Since motion sensors are not being evaluated for diagnostic purposes or being studied themselves within the context of this protocol and are only intended to collect physiological data, they are not to be considered investigational. The data collected in this feasibility study will not contain any personally identifiable information (PII). In this study, healthy participants will complete a total of approximately 18 measured breaths through a traditional incentive spirometer while wearing small, non-invasive motion sensors on their thorax at approximately the level of the 9 th and 10 th ribs unilaterally or bilaterally. The incentive spirometer is an FDA approved medical device. This study does not aim to study the safety or effectiveness of this device but rather utilize the device as a tool to measure volume of inspiration. The waveform data collected from the devices with each breath will then be analyzed with the intention to develop an algorithm that could convert chest wall motion to a discrete volume of inspiration in real time. Total enrollment time will be about 10-30 minutes per participant.
Objectives:	
Primary:
 
To collect chest wall motion data corresponding to various volumes of inspiration from a non-invasive wearable device.
 
Secondary:
 
To develop an algorithm which can convert chest wall motion to volume of inspiration and assess the algorithm using cross-validation strategy.

Endpoints:	
Primary:
 
A database of motion waveforms corresponding to each measured volume of inspiration via traditional incentive spirometer.
 
Secondary:
 
A cross-validated algorithm that converts chest wall motion to volume of inspiration.

Study Population:	Healthy volunteers of both sex and demographic groups who are ages 18 and older.

Abbreviated Title: Wearable Incentive Spirometry

Version Date: 09/08/2025

[figure not shown]
Description of Sites/Facilities Enrolling Participants: All participants will be healthy volunteers recruited at the NIH.

Study Duration: 1 month

Participant Duration: 15-30 minutes

1.2 SCHEMA

Participation Flow Diagram

Flow diagram alt text:

- Participants will be consented at the start of the meeting and provided a study ID to ensure patient confidentiality.
- Each participant will then fill out a form with their study ID, age, sex, height, weight.
- The small motion sensor will then be placed unilaterally or bilaterally on the patient's thorax at approximately the level of the 9th and 10th ribs at the mid-axillary line using hypoallergenic double-sided adhesive tape.
- With the motion sensor in place, the participant will then take breaths through a traditional FDA approved incentive spirometer. They will ideally complete three breaths at each of the following volumes: 250mL, 500mL, 1000mL, 1500mL, 2000mL, and 2500mL.
- Upon completion, the motion sensor will be removed, and the participant will be free to go with no future scheduled appointments or follow-up.

INTRODUCTION

1.3 STUDY BACKGROUND AND RATIONALE

Postoperative pulmonary complications (PPCs) encompass a broad and heterogenous spectrum of conditions which serve as a leading cause of suboptimal surgical outcomes globally.

Approximately 10-20% of the 310 million patients undergoing surgery each year will develop a PPC [1-6], and up to 25% of all deaths occurring within one week post-operatively attributed to PPCs [4]. These pulmonary complications, which range from minor respiratory alterations to severe conditions like pneumonia or respiratory failure, are a culmination of changes to the respiratory system that begin immediately after induction of general anesthesia. While under general anesthesia, patients experience decreased respiratory drive, reduced lung volumes, and altered ventilation perfusion relationship. The addition of a neuromuscular blocking drug for general anesthesia further increases risk for PPC with up to 75% of patients developing some degree of atelectasis post-operatively [7, 8]. The pain and fatigue many patients encounter post-operatively amplify the risk of PPCs, as patients become more hesitant to take deep, lung-expanding breaths. Considering these elements, it stands to reason that PPCs substantially influence prolonged hospital stays, elevated healthcare expenditures, and a deterioration in holistic patient outcomes.

Incentive spirometry (IS) has traditionally served as a cornerstone in the prophylaxis and management of PPCs. The incentive spirometer works by emulating a natural deep breath, serving simply as a visual tool for both patients and providers to gauge the quality and depth of lung expansion. The device does not offer any added resistance to assist in alveoli opening. By promoting voluntary deep breathing, the device helps to improve pulmonary function, maintain alveolar inflation, and enhance the clearance of secretions [9-11]. Despite its widespread acceptance in clinical practice, recent literature has shed light on various limitations associated with conventional incentive spirometry [12, 13]. Some of these drawbacks include patient compliance, nursing burden, and the lack of data storage for longitudinal tracking. Without a means to quantitatively assess patient effort and progress, it becomes difficult to assess the true impact of incentive spirometry on patient outcomes.

The continual advancements of digital health technologies and artificial intelligence present a compelling opportunity to address these gaps. Some efforts have been made by other groups to correlate chest wall motion with lung function, particularly in the asthma and apnea monitoring spaces. One group was successful in measuring respiration rate and lung volume using wearable strain sensors on a small cohort of volunteers. Others have detected respiratory rate via acoustic adhesive sensors on the neck [14] or detected changes in respiratory effort during sleep via an elastic band around the thorax and corresponding sensor measuring stretch patterns [15]. It is possible that we might identify unique patterns in chest wall motion via motion sensors adhered to the patient's thorax to easily measure and track volume of inspiration and respiratory effort post-operatively. This technology could open a door to improved IS compliance and may result in decreased nursing burden and improved post-operative management. If successful, it is possible that a wearable motion sensor could serve as a substitute for incentive spirometry with features to improve patient compliance, facilitate longitudinal IS data collection, and reduce burden on nursing staff who continuously have to provide incentive spirometers and remind patients to use them.

1.4 RISK/BENEFIT ASSESSMENT

1.4.1 Known Potential Risks

There only known risk to the participant is the development of a skin reaction or allergy to the hypoallergenic double-sided tape. Participants included in this study will be screened and excluded for known allergies to adhesives to mitigate this risk.

1.4.2 Known Potential Benefits

This study may not benefit specific study participants, but the results may help the investigators learn about the use of motion sensors to improve recording and tracking of post-operative incentive spirometry exercises and may potentially aid in post-operative management of future patients.

1.4.3 Assessment of Potential Risks and Benefits

The potential knowledge that may result from this study is considerable and may balance any potential risks to the participants. Proving that it is possible to detect volume of inspiration and respiratory rate from a non-invasive, wearable motion sensor could inform future studies which might work to improve IS compliance, data transmission, longitudinal tracking, and nursing burden.

OBJECTIVES AND ENDPOINTS

OBJECTIVES	ENDPOINTS	JUSTIFICATION FOR ENDPOINTS
Primary		
To collect chest wall motion data corresponding to various volumes of inspiration from a non-invasive wearable device.	A database of motion waveforms corresponding to each measured volume of inspiration via traditional incentive spirometer.	The primary goal of this study is to collect data to correlate changes in chest wall motion with volume of inspiration. The first step in doing so is the creation of a database with this information.
Secondary		
To develop an algorithm which can convert chest wall motion to volume of inspiration and assess the algorithm using cross-validation strategy.	A cross-validated algorithm that converts chest wall motion to volume of inspiration.	This endpoint will allow us to prove the ability to calculate volume of inspiration from chest wall motion and assess its accuracy.

STUDY DESIGN

1.5 OVERALL DESIGN

Healthy volunteers (n = 30) will be recruited for participation in this proof-of-concept study. Each participant will be consented and assigned a study number to ensure that all data is non-PII. Participants will be asked to fill out a de-identified form with their age, sex, height and weight prior to application of motion sensor (see section **1.6**).

Each participant will wear the devices for approximately 10-30 minutes while they perform a series of breathing exercises. The thoracic wearable will be adhered unilaterally or bilaterally at approximately the level of the 9th and 10th ribs at the mid-axillary line. Hypoallergenic double-sided tape will be used to adhere the motion sensor to the volunteers' torso in this position. The participant will ideally take three breaths through a traditional incentive spirometer while wearing the devices at each of the following volumes: 250mL, 500mL, 1000mL, 1500mL, 2000mL, and 2500mL. Each breath will be held for approximately 5 seconds before being released. Throughout this period, the thoracic wearable will be detecting chest wall expansion. All data will be transmitted to a secure server located within the NIH clinical center for analysis and model creation. Upon completion of the breathing exercises, the device will be removed from the participant, and the participant will be free to leave. There will be no further study visits or contact required.

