1.26 STUDY EVALUATIONS & PROCEDURES

All patients consented for participation will undergo the following procedures:

1. Recording self-reported age, sex, height, and weight.
2. Application of the motion sensor using a medical grade double sided adhesive.
3. While seated, each participant will ideally take three breaths at each of the following volumes through a traditional FDA approved incentive spirometer: 250mL, 500mL, 1000mL, 1500mL, 2000mL, and 2500mL. The participants will hold each breath for approximately 5 seconds before exhaling.
4. Data collection will include motion data transmitted from the motion sensor to a secure NIH server.

Abbreviated Title: Wearable Incentive Spirometry

Version Date: 09/08/2025

None of this data will be transmitted back to the participants themselves. All findings associated with this study will, however, be made publicly available upon the completion of this study.

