1.31 SAMPLE SIZE DETERMINATION

We hope to recruit approximately 30 participants for initial proof-of-concept data collection.

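### With one sensor application per participant, placement variation cannot be separated from anatomical differences, and performance after re-application is not tested

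*Combined protocol and SAP*

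**What the plan says.** The procedures in section 1.26 contain one application step, "Application of the motion sensor using a medical grade double sided adhesive", followed by the breathing series. According to the Synopsis, "healthy participants will complete a total of approximately 18 measured breaths through a traditional incentive spirometer". Section 1.5 then ends the session: "Upon completion of the breathing exercises, the device will be removed from the participant, and the participant will be free to leave", and "There will be no further study visits or contact required". Section 1.17.1 describes the same sequence. No section describes taking the sensor off and putting it back on the same person.

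Placement is loosely specified in section 1.5: "The thoracic wearable will be adhered unilaterally or bilaterally at approximately the level of the 9th and 10th ribs at the mid-axillary line". Section 1.17.1 makes the mid-axillary line approximate as well. No tolerance is given, and there is no rule for choosing one side or both.

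On use, section 1.4.2 speaks of "the use of motion sensors to improve recording and tracking of post-operative incentive spirometry exercises", and section 1.3 hopes that a wearable could "facilitate longitudinal IS data collection". Section 1.4.3 leaves longitudinal tracking to future studies. The objectives are a waveform database and a cross-validated algorithm.

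On analysis, section 1.33.3 names stratified K-fold as an example of the cross-validation and plans a held-out test set, but does not say whether the fold unit is the breath or the participant. Section 1.33.5 asks whether sex and BMI affect chest wall motion at each volume.

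**The concern.** The relation between chest wall motion and inspired volume may differ between two people because their chests differ or because their sensors sit in slightly different places. With one application each, every person carries exactly one placement, and the two sources cannot be told apart. Tighter placement instructions would reduce the placement part but would not measure it.

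Two things follow. In the sex and BMI analysis, the spread that these factors leave unexplained is anatomy plus placement in unknown proportion. And no breath tests whether the learned relation holds once the sensor has been moved. That matters for the next study. If the between-person spread is mostly anatomical, a calibration made once per wearer could last. If it is mostly placement, it would have to be repeated at each application. If cross-validation also puts breaths from one participant's single application in both training and test sets, the reported error will not contain the placement component at all.

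**Working it through.** **Inputs from the documents.** About 30 participants (section 1.31: "We hope to recruit approximately 30 participants for initial proof-of-concept data collection"), one application each (sections 1.5, 1.17.1, 1.26), and about 18 breaths each (Synopsis). The breath count reproduces: 6 volumes x 3 breaths = 18. The sample size has no stated derivation, so there is nothing to reproduce there. No breath, person or placement variance is given, so every SD and CV below is an assumption.

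**Step 1: can placement be separated from anatomy?** Write log(motion per litre) = person + placement + breath noise. Degrees of freedom for placement are N x (applications - 1) = 30 x (1 - 1) = 0, and the result is 0 for any N. The expected variance of participant means is person² + placement² + breath²/18. With breath SD 0.10 the last term is 0.01/18 = 0.0006.

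| Person SD | Placement SD | Sum of squares | Plus breath term |
|---|---|---|---|
| 0.25 | 0 | 0.0625 | 0.063 |
| 0.20 | 0.15 | 0.0400 + 0.0225 = 0.0625 | 0.063 |
| 0.15 | 0.20 | 0.0225 + 0.0400 = 0.0625 | 0.063 |
| 0 | 0.25 | 0.0625 | 0.063 |

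A simulation of the design (2,000 runs) gave 0.063 to 0.064 in all four cases. The data cannot tell all anatomy from all placement.

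**Step 2: what would the reported error contain?** This depends on the fold unit. With breath SD 0.10, on the log scale:

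- Breaths of one participant split across folds: sqrt(0.01 x (1 + 1/17)) = 0.103, whatever the placement SD.
- Same person re-applied, using the calibration from the first application: sqrt(2 x placement² + 0.01 x (1 + 1/18)). For placement SD 0, 0.05, 0.10 and 0.20 this is 0.103, 0.125, 0.175 and 0.301.
- Whole participants held out (simulated): 0.29 at person/placement SD 0.25/0.10, against 0.17 for the re-applied, personally calibrated wearer. At 0.15/0.20 it is 0.27 against 0.30.

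So splitting breaths within a participant is over-favourable for re-application whenever placement variance exceeds zero. Holding out participants is over-favourable only when placement variance exceeds person variance. Otherwise it is conservative.

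**Step 3: illustration in mL.** Suppose volume is predicted from one reference breath, a procedure the plan does not contain. Same-application relative error is sqrt(2b²) and re-applied error is sqrt(2b² + 2r²), where b is breath CV and r is placement CV. At 2000 mL:

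| b | Same application | r = 5% | r = 10% | r = 20% | Ratio |
|---|---|---|---|---|---|
| 5% | 141 mL | 200 mL | 316 mL | 583 mL | 1.4, 2.2, 4.1 |
| 10% | 283 mL | 316 mL | 400 mL | 632 mL | 1.1, 1.4, 2.2 |

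With r = 0 the ratio is 1.0.

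**Step 4: what one re-application would give.** With all 30 re-applied once, the degrees of freedom are 30 x (2 - 1) = 30. The 95% interval for the SD of the total within-person change runs from sqrt(30/46.98) = 0.80 to sqrt(30/16.79) = 1.34 times the estimate. For a subset of 15 it is 0.74 to 1.55 times, and for 10 it is 0.70 to 1.75 times. These are best cases. The interval covers the total change, including breath noise, so the placement component alone is known less precisely.

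**The case against.** The strongest reply is that this is a first proof of concept whose objectives are a database and a cross-validated algorithm. Tracking across applications is a later use, which section 1.4.3 leaves to future studies, and section 1.8 sends further work to a new protocol. No text claims accuracy after re-application. That stands: the point is a limit on what can be concluded, and the plan does not contradict itself.

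It can also be said that the plan contains no reference-breath calibration and no repeatability statistic, so the study would never report the same-application figures in the mL table. That stands too. The table shows direction and sensitivity to assumptions and does not forecast this study's output.

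A reader might infer that the reported accuracy will necessarily overstate what repeated tracking can achieve. The documents do not support that. It needs breaths from one participant's single application on both sides of the split, placement variance above zero, and no recalibration at later applications. Section 1.33.3 permits the first without stating it, and the other two are open. If whole participants are held out, the error already includes placement and may even understate tracking with personal calibration.

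Bilateral wear does not answer the point: it is optional, both sensors are worn at once, and any difference between them is mixed with left-right asymmetry.

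**Conclusion.** The confounding is certain and follows from the procedures alone: one application per person leaves placement with no degrees of freedom at any sample size, and no reanalysis recovers it. The effect on reported accuracy is conditional. It is over-favourable for re-application if folds split a participant's breaths. If participants are held out whole, placement is included but unidentified. The size is unknown because the documents give no variances. Under the assumed CVs the understatement factor runs from 1.0 (no placement variation), through 1.1 to 2.2 (breath CV 10%), to 1.4 to 4.1 (breath CV 5%). This is a worthwhile improvement to the design, not an error that invalidates the study's stated objectives.

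**What to change.** In sections 1.5, 1.17.1 and 1.26, take the planned three breaths per volume as three passes through the volume list. Remove and re-apply the sensor once at the same landmark, before pass 2 in half of the participants and before pass 3 in the other half. Re-applying always before the last pass would mix placement with order effects such as learning or fatigue. Under the split, everyone who completes three passes supplies one same-application and one across-application comparison. Section 1.17.1 lists seven volumes where sections 1.2, 1.5 and 1.26 list six. These lists need to be reconciled before the passes are written.

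In section 1.33.3:

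- Keep all of a participant's breaths in one fold.
- Report the within-person change in motion per litre across applications, net of breath-to-breath variation, beside the between-person SD.
- Note that same-day re-application may understate day-to-day variation.
- State how many participants supplied breaths under both applications. Section 1.7 accepts one attempt per volume, and anyone with a single pass contributes nothing here and widens the interval.

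If re-application is not adopted, limit accuracy statements to a single sensor application. The fold rule is worth adopting either way.

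The cost is a short amendment, a few more minutes, and a second adhesive contact per participant. That contact is relevant because section 1.4.1 names skin reaction to the tape as the only known risk. No extra breaths, visits or staff are needed.

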1.6 SCIENTIFIC RATIONALE FOR STUDY DESIGN

This is a basic physiologic proof-of-concept study to determine the feasibility of using a motion sensor to indirectly measure volume of inspiration. As such, there is no control group. The study design is appropriate to meet the goals of this study which are to acquire motion data from people taking measured breaths through traditional incentive spirometer.

1.7 JUSTIFICATION FOR INTERVENTION

The entire duration of study participation is 10-30 minutes, making this an incredibly low-commitment study for healthy volunteers. Minimum acceptable study participation is completion of the demographic information at least one attempt of all measured lung volumes, as it is possible that some participants will not be capable of taking the maximal volume of inspiration.

1.8 END-OF-STUDY DEFINITION

A participant is considered to have completed the study if he or she has completed the demographic form and attempted all volumes of inspiration with the motion sensor in place.

Should the results of this basic physiologic proof-of-concept study be successful, future analysis of the technology developed (algorithm) would be submitted under a new IDE protocol to perform a study on a larger scale using this device and the algorithm which would be developed and marketed to assist in diagnosis, likely be considered a medical device at that time beholden to 21 CFR 812, used off label and likely would be NSR along with the algorithm that is developed.

